11.2 STATEMENT OF CONFIDENTIALITY

Upon PraxbindTM administration, anonymized patient data will be collected. Every site participating in the surveillance program should collect the patient data anonymously. No data will be key-coded to the patient's identity.

Treatment data may be given to the patient's personal physician or to other appropriate medical personnel responsible for the patient's welfare. Data generated as a result of the study need to be available for inspection on request by the participating physicians, the sponsor's representatives, by the IRB / IEC and the regulatory authorities.

12. MANAGEMENT AND REPORTING OF ADVERSE EVENTS/ADVERSE REACTIONS

12.1 DEFINITIONS OF ADVERSE EVENTS

Adverse event

An adverse event (AE) is defined as any untoward medical occurrence in a patient or clinical investigation subject administered a medicinal product and which does not necessarily have a causal relationship with this treatment. An adverse event can therefore be any unfavourable and unintended sign (e.g. an abnormal laboratory finding), symptom, or disease temporally associated with the use of a medicinal product, whether or not considered related to the medicinal product.

Adverse reaction

An adverse reaction is defined as a response to a medicinal product which is noxious and unintended. Response in this context means that a causal relationship between a medicinal product and an adverse event is at least a reasonable possibility. Adverse reactions may arise from use of the product within or outside the terms of the marketing authorization or from occupational exposure. Conditions of use outside the marketing authorization include off-label use, overdose, misuse, abuse and medication errors.

Serious adverse event

A serious adverse event is defined as any AE which

- results in death,
- is life-threatening,
- requires in-patient hospitalization, or
- prolongation of existing hospitalisation,
- results in persistent or significant disability or incapacity, or
- is a congenital anomaly/birth defect

Life-threatening in this context refers to a reaction in which the patient was at risk of death at the time of the reaction; it does not refer to a reaction that hypothetically might have caused death if more severe.

Medical and scientific judgement should be exercised in deciding whether other situations should be considered serious reactions, such as important medical events that might not be immediately life threatening or result in death or hospitalization but might jeopardize the patient or might require intervention to prevent one of the other outcomes listed above. Examples of such events are intensive treatment in an emergency room or at home for allergic bronchospasm, blood dyscrasias or convulsions that do not result in hospitalization or development of dependency or abuse.

Adverse Event of Special Interest (AESI)

The term Adverse Event of Special Interest (AESI) relates to any specific AE that has been identified at the project level as being of particular concern for prospective safety monitoring

and safety assessment within this study, e.g. the potential for AEs based on knowledge from other compounds in the same class.

No AESIs have been defined for this study.

12.2 ADVERSE EVENT AND SERIOUS ADVERSE EVENT COLLECTION AND REPORTING

The investigator shall maintain and keep detailed records of all AEs in their patient files.

Collection of AEs

The study design is of non-interventional nature and the study is conducted within the conditions of the approved marketing authorization. Sufficient data from controlled interventional trials are available to support the evidence on the safety and efficacy of the studied BI drug. For this reason the following AE collection and reporting requirements have been defined.

The following must be collected by the investigator in the (e) CRF from signing the informed consent onwards until the end of the study:

- all adverse drug reactions (ADRs, serious and non-serious) associated with PraxbindTM,
- all AEs with fatal outcome in patients exposed to PraxbindTM.

All ADRs, including those persisting after study completion must be followed up until they are resolved, have been sufficiently characterized, or no further information can be obtained.

The investigator carefully assesses whether an AE constitutes an ADR using the information below.

Causal relationship of adverse event

The definition of an adverse reaction implies at least a reasonable possibility of a causal relationship between a suspected medicinal product and an adverse event. An adverse reaction, in contrast to an adverse event, is characterized by the fact that a causal relationship between a medicinal product and an occurrence is suspected.

Medical judgment should be used to determine the relationship, considering all relevant factors, including pattern of reaction, temporal relationship, de-challenge or re-challenge, confounding factors such as concomitant medication, concomitant diseases and relevant history.

Arguments that may suggest a **reasonable causal relationship** could be:

- The event is **consistent with the known pharmacology** of the drug
- The event is known to be caused by or **attributed to the drug class**.
- **A plausible time to onset of the event** relative to the time of drug exposure.
- Evidence that the **event is reproducible** when the drug is re-introduced
- **No medically sound alternative etiologies** that could explain the event (e.g. preexisting or concomitant diseases, or co-medications).

- The event is typically **drug-related and infrequent in the general population** not exposed to drugs (e.g. Stevens-Johnson syndrome).
- An indication of dose-response (i.e. greater effect size if the dose is increased, smaller effect size if dose is diminished).

Arguments that may suggest that there is **no reasonable possibility of a causal relationship** could be:

- No plausible time to onset of the event relative to the time of drug exposure is evident (e.g. pre-treatment cases, diagnosis of cancer or chronic disease within days/weeks of drug administration; an allergic reaction weeks after discontinuation of the drug concerned)
- Continuation of the event despite the withdrawal of the medication, taking into account the pharmacological properties of the compound (e.g. after 5 half-lives). Of note, this criterion may not be applicable to events whose time course is prolonged despite removing the original trigger.
- Additional arguments amongst those stated before, like alternative explanation (e.g. situations where other drugs or underlying diseases appear to provide a more likely explanation for the observed event than the drug concerned).
- Disappearance of the event even though the study drug treatment continues or remains unchanged.

Intensity of adverse event

The intensity of the AE should be judged based on the following:

Mild: Awareness of sign(s) or symptom(s) which is/are easily tolerated

Moderate: Enough discomfort to cause interference with usual activity

Severe: Incapacitating or causing inability to work or to perform usual activities

The intensity of adverse events should be classified and recorded according to the Common Terminology Criteria for Adverse Events (CTCAE) criteria in the (e) CRF.

Pregnancy:

In rare cases, pregnancy might occur in a study. Once a subject has been enrolled into the study, after having taken PraxbindTM, the investigator must report any drug exposure during pregnancy, which occurred in a female subject or in a partner to a male subject to the Sponsor by means of Part A of the Pregnancy Monitoring Form. The outcome of the pregnancy associated with the drug exposure during pregnancy must be followed up and reported by means of Part B of the Pregnancy Monitoring Form.

In the absence of a reportable AE, only the Pregnancy Monitoring Form must be completed, otherwise the NIS AE form is to be completed and forwarded as well within the respective timelines.

Expedited Reporting of AEs and Drug Exposure During Pregnancy

BI

The following must be reported by the investigator on the NIS AE form from signing the informed consent onwards until the end of the study:

Type of Report	Timeline
All serious ADRs associated with Praxbind™	immediately within 24 hours
All AEs with fatal outcome in patients exposed to Praxbind™	immediately within 24 hours
All non-serious ADRs associated with Praxbind™	7 calendar days
All pregnancy monitoring forms	7 calendar days

The same timelines apply if follow-up information becomes available for the respective events. In specific occasions the Investigator could inform the Sponsor upfront via telephone. This does not replace the requirement to complete and fax the NIS AE form.

Information required

For each reportable adverse event, the investigator should provide the information requested on the appropriate (e)CRF pages and the NIS AE form.

Reporting of the indication for which Praxbind™ is used

For patients not participating in 1160.189 or 1160.248, the investigator must report the indication for which Praxbind™ is used (emergency surgery/urgent procedures or life-threatening or uncontrolled bleeding) as spontaneous Pradaxa (dabigatran etexilate) case to the above mentioned BI contact for AE/Pregnancy Reporting. For emergency surgery/urgent procedures the underlying condition requiring the surgery/procedure must be indicated in the report.

This reporting obligation is independent of causality assessment, but a causality assessment must always be provided.

Proprietary confidential information © 2018 Boehringer Ingelheim International GmbH or one or more of its affiliated companies

For patients participating in 1160.189 or 1160.248, the reporting of the indication for which Praxbind™ is used must occur within those trials following the requirements for 1160.189 or 1160.248 respectively.

Reporting of related Adverse Events associated with any other BI drug

The investigator is encouraged to report all adverse events related to any BI drug other than Praxbind™ according to the local regulatory requirements for spontaneous AE reporting at the investigator's discretion by using the locally established routes and AE report forms. The term AE includes drug exposure during pregnancy, and, regardless of whether an AE occurred or not, any abuse, off-label use, misuse, medication error, occupational exposure, lack of effect, and unexpected benefit.

(If the event associated to the indication for Praxbind™ is considered related to Pradaxa (dabigatran etexilate), see section "Reporting of the indication for which Praxbind™ is used").

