## **5 CHANGES IN THE PLANNED ANALYSIS OF THE STUDY**

No changes made in the planned analysis of the study mentioned in the protocol version 3.0, dated 13 Sep 2017.

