## **6.4 OTHER VARIABLES**

In this study, the following variables will be considered.

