- Dosage and administration (total dose administered and time interval between the administration of the two vials; vials to be taken one after the other, immediate administration of the second vial is mandatory);
- Premature PraxbindTM administration discontinuation (yes/no).
- In case if the patient requires an additional 5 g dose for the following conditions as per the label:
  - i. recurrence of clinically relevant bleeding together with prolonged clotting times, or
  - ii. if potential re-bleeding would be life-threatening and prolonged clotting times are observed, or
  - iii. patients require a second emergency surgery/urgent procedure and have prolonged clotting times.
- Information on restart of anticoagulation therapy (which anticoagulation treatment including dose and when was it restarted).
- All adverse drug reactions (ADRs, serious and non-serious) associated with PraxbindTM.
- All AEs with fatal outcome in patients exposed to PraxbindTM.

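### Required AE data cover only ADRs and fatal AEs from consent onwards, but the SAP plans six wider AE tables and a causality split, and the 7-day primary window starts at administration

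*Protocol*

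**What the plan says.** Protocol 12.2 keeps the adverse event data small on purpose. It argues that controlled trials already support the drug's safety and efficacy, and continues: "For this reason the following AE collection and reporting requirements have been defined". Two classes follow: "all adverse drug reactions (ADRs, serious and non-serious) associated with PraxbindTM", and AEs with a fatal outcome. The period is set by "The following must be collected by the investigator in the (e) CRF from signing the informed consent onwards until the end of the study". Expedited reporting in the same section covers the same two classes (plus pregnancy forms) with the same start: they "must be reported by the investigator on the NIS AE form from signing the informed consent onwards". The one wider duty in 12.2 concerns site files, not the e-CRF: "The investigator shall maintain and keep detailed records of all AEs in their patient files".

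The SAP's variable list (6.4), introduced by "In this study, the following variables will be considered", repeats the pair: ADRs, and "All AEs with fatal outcome in patients exposed to Praxbind". SAP 5 states "No changes made in the planned analysis of the study mentioned in the protocol version 3.0".

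SAP 8.8 then names three targets for the safety analysis: suspected ADRs, serious AEs, and AEs leading to death. The second has no causality limit. SAP 8.8.1 sorts events into serious, non-serious, death and withdrawal, splits each by causal relationship, and lists 10 summary tables. It treats an event as an ADR when either the reporting physician or the sponsor judges it related. It also says that the listings rest on what the eCRF captured.

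The primary outcome (Protocol 10.2.2.1; SAP 6.1 and 8.4) is suspected ADRs and fatal AEs in the 7 days after administration.

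**The concern.** There are two separate questions.

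The first is scope. A table titled as a summary of serious AEs will be read as exactly that. If the data behind it hold only serious ADRs and deaths, the count is too low for its title whenever an unrelated non-fatal SAE has occurred. An empty cell for unrelated non-serious events would look like a finding, when the collection rule produced it. ADRs and fatal AEs are the special focus of the main objective (Protocol 9), so these tables will be read closely.

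The second is timing. The clock for the primary outcome starts at dosing, and the duty to collect starts at consent. The drug is given for emergency surgery or life-threatening bleeding (Protocol 10.1.2), so whether written consent is in hand before dosing is a practical question. If it is not, the first part of the primary window lies outside required collection.

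**Working it through.** The plan gives no figure on this point to reproduce. The check sets the sections side by side, with simple counting.

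**1. Scope of the ten tables in SAP 8.8.1**

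| Table | Limited to ADRs or fatal AEs? |
|---|---|
| Overall | No |
| SOC and PT | No |
| Maximum severity | No |
| Related AEs | Yes (ADRs) |
| Serious AEs | No |
| Deaths | Yes (fatal) |
| Related serious AEs | Yes (ADRs) |
| Related non-serious AEs | Yes (ADRs) |
| Discontinuation | No |
| Dose reduction | No |

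Four match the collected classes, and 10 − 4 = 6 do not. The serious table is listed apart from the related serious table, so it cannot be meant as serious ADRs.

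**2. Causality split, assuming sites enter only the 12.2 minimum**

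Four categories × two causality levels = 8 cells. A collected event is investigator-related or fatal. Protocol 12.1 makes every fatal event serious. The four not-related cells are then:

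- Non-serious: a collected event that is not related must be fatal, and so serious. The cell is always 0.
- Serious: fatal events only, so it equals the unrelated deaths.
- Death: the unrelated deaths.
- Withdrawal: fatal events only.

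Three of the four hold nothing beyond unrelated deaths, and every non-fatal event is related by rule. An event that only the sponsor calls related is collected only if it is fatal, and fatal AEs are already in the primary outcome. Under this assumption the sponsor half of the ADR definition adds 0 events.

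**3. Order of consent and dosing**

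- Pointing to consent first: Protocol 10.1.2 (consent is an inclusion criterion), Protocol 11.1 (consent before participation), and SAP 7.3 (treated patients are a subset of entered patients, who are a subset of those who signed).
- Leaving it open: Protocol 10.1 (the program enrols patients administered the drug) and the pregnancy paragraph of 12.2 (enrolment mentioned together with having already taken the drug).
- No section states the order outright.

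**4. Share of the window before required collection**

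The window is 7 × 24 = 168 h. Share = delay / 168. The documents give no delay, so these values are assumptions:

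| Consent after dosing | Share of window |
|---|---|
| 0 h, or consent first | 0% |
| 12 h | 12/168 = 7.1% |
| 24 h | 24/168 = 14.3% |
| 48 h | 48/168 = 28.6% |
| 72 h | 72/168 = 42.9% |

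These are shares of time, not of events. The number of events missed cannot be derived.

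**The case against.** The scope results depend on a document that is not available. SAP 4 cites CRF Final version 3.0. Protocol 12.2 says what must be collected and does not forbid more, and Protocol 10.9.2.1 lists AEs and SAEs among the e-CRF data without limit. If the CRF takes all AEs, the six titles are accurate and the split is informative. This stands, and it lowers confidence. It does not remove the problem: 10.9.2.1 can also be read within the scope of 12.2, and sites that read it differently would put two capture rules into one table.

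The SAP also has its own safeguards. Its listings rest on what the eCRF captured. SAP 8 lists all data by patient, for at most 25 patients, and puts a comment in place of a summary with no data. So the tables can be produced and each entered event can be inspected. But listings show only what was entered, and nothing planned tells the reader that an empty cell comes from the collection rule.

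The no-change statement in SAP 5 adds little to the point. Protocol 10.6.1 plans descriptive statistics and specifies no AE tables, so the SAP's list does not contradict it. It is also true that the cell results in step 2 follow directly from the assumption. They show what a reader would see, not that events have been lost.

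On timing, Protocol 11.1 allows consent by a legally accepted representative, which makes consent before dosing more feasible. Protocol 10.2 lists both event classes with no consent start, 10.3 draws data from notes and hospital records, and 11.2 has data collected upon administration. These support coverage from dosing in practice. However, 12.2 is where the obligation is dated, and it dates it from consent.

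**Conclusion.** The mismatch is in the text. If sites enter only the 12.2 minimum, six of ten AE tables can understate the incidence that their titles name, and the causality split says nothing about non-fatal events. This is a fault of labelling and interpretation. The timing gap is conditional: it is 0% of the window if consent comes first and of unknown effect if it does not. Severity is minor to moderate and confidence is moderate.

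A reader might infer more than the documents support:

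- That the scope limit biases the primary outcome. It does not: the primary outcome consists of the two classes that are collected. The idle sponsor clause limits what the SAP's ADR rule can do, but it is not a demonstrated under-count.
- That the restriction itself is wrong. Protocol 12.2 gives a reason for it, which is not disputed here.
- That early events are being lost. This needs consent after dosing, which no section states and several suggest is not intended. Even then it concerns only patients who do consent. Those who die before any consent are a separate question of selection.

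**What to change.** 1. **Protocol 12.2, collection and expedited reporting.** Start both at the earlier of consent or first Praxbind administration. Events before consent are taken from the notes once consent is given, and marked as retrospective. Using the earlier of the two keeps the consent-to-dosing interval that 12.2 covers now; a start at administration alone would drop it.
2. **SAP 8.8 and 8.8.1.** Replace serious AEs in 8.8 with serious ADRs and fatal AEs. Retitle the six tables as covering ADRs and fatal AEs. Add one footnote: non-fatal AEs judged unrelated are not required to be collected, so the causality split is uninformative for non-fatal AEs, and sponsor causality acts only on collected events.
3. **Protocol 10.9.2.1.** Refer both adverse event lines to the scope of 12.2.

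The cost is wording: two sentences in 12.2, one cross-reference, and one phrase, six titles and a footnote in the SAP. No event class is added. For patients consented after dosing, sites look back through notes that are already the data source (Protocol 10.3), in at most 25 patients. The downside is that events taken from notes may be less complete than those collected prospectively. Patients who die before any consent are still not recovered.

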12.3 REPORTING TO HEALTH AUTHORITIES

Adverse event reporting to regulatory agencies will be done by the MAH according to local and international regulatory requirements.

13. PLANS FOR DISSEMINATING AND COMMUNICATING STUDY RESULTS

The rights of the investigator and of the sponsor with regard to publication of the results of this study are described in the investigator contract. As a general rule, no study results should be published prior to finalization of the Study Report.

ANNEX 1. LIST OF STAND-ALONE DOCUMENTS

None

ANNEX 2. ENCEPP CHECKLIST FOR STUDY PROTOCOLS

EUROPEAN MEDICINES AGENCY
SCIENCE MEDICINES HEALTH

European Network of Centers for
Pharmacoepidemiology and
Pharmacovigilance

Doc.Ref. EMA/540136/2009

ENCePP Checklist for Study Protocols (Revision 3)

Adopted by the ENCePP Steering Group on 01/07/2016

The European Network of Centers for Pharmacoepidemiology and Pharmacovigilance (ENCePP) welcomes innovative designs and new methods of research. This Checklist has been developed by ENCePP to stimulate consideration of important principles when designing and writing a pharmacoepidemiological or pharmacovigilance study protocol. The Checklist is intended to promote the quality of such studies, not their uniformity. The user is also referred to the ENCePP Guide on Methodological Standards in Pharmacoepidemiology, which reviews and gives direct electronic access to guidance for research in pharmacoepidemiology and pharmacovigilance.

For each question of the Checklist, the investigator should indicate whether or not it has been addressed in the study protocol. If the answer is "Yes", the section number of the protocol where this issue has been discussed should be specified. It is possible that some questions do not apply to a particular study (for example, in the case of an innovative study design). In this case, the answer 'N/A' (Not Applicable) can be checked and the "Comments" field included for each section should be used to explain why. The "Comments" field can also be used to elaborate on a "No" answer.

This Checklist should be included as an Annex by marketing authorisation holders when submitting the protocol of a non-interventional post-authorisation safety study (PASS) to a regulatory authority (see the Guidance on the format and content of the protocol of non-interventional post-authorisation safety studies). The Checklist is a supporting document and does not replace the format of the protocol for PASS as recommended in the Guidance and Module VIII of the Good pharmacovigilance practices (GVP).

Study title:

Post marketing surveillance program of PraxbindTM use in India.

Study reference number:

1321-0023

Section 1: Milestones	Yes	No	N/A	Section Number
